10.2.1 Patient Reported Outcomes

Received MDASI-BT form will be checked versus the timing schedule and considered as valid if they fall within ten days of the scheduled assessment window. Compliance rates will be calculated as the number of received valid forms over the number of expected forms. Differences between groups in compliance will be tested by use of Fisher’s exact test at every time point.

We will use descriptive statistics to describe how patients rate symptom severity and interference with function at each time point. Error bar graphs for each of the symptoms will be constructed at each time point. The proportion of patients rating their symptoms to be 5 or greater (on a 0-10 scale) will also be reported. We will construct individual patient profiles for each of the selected symptoms to describe the individual patients’ patterns of change over time. We will calculate the mean symptom severity, and mean symptom interference at the time of clinical evaluation.

Estimates of differences in the mean symptom severity and mean symptom interference between responders and non-responders will be estimated in the intent to treat population. All patients

with at least one valid questionnaire will be included in the analyses. Questionnaires completed at study registration will be considered baseline. All questionnaire data received after randomization will be used in the primary analyses.

Differences of at least 2 points will be classified as the minimum clinically meaningful change in the symptom severity and symptom interference measures. For example, an increase of 2 points or more would mean a moderate improvement, whereas a decrease of 2 points or more would be interpreted as moderate worsening. For individual symptoms, a rise in a symptom score means deterioration, whereas a reduced score means improvement of the specific symptom.

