3.4 QUESTIONNAIRES

3.4.1 MD Anderson Symptom Inventory-Brain Tumor (MDASI-BT):

The MDASI-BT will be administered at baseline and at the time of imaging analysis as outlined in the protocol. Of note, every attempt should be made to administer the MDASI-BT prior to informing the patients about the results of the imaging study. The MDASI-BT will be completed only by the patient, unless changes in vision or weakness make this difficult. If this occurs, then the caregiver or research assistant may read the questions to the patient or assist with marking the severity number or score as described by the patient. A caregiver may complete the questionnaires as a patient proxy if the patient's deficits preclude self-report; however, this must be done at every assessment from baseline to end of treatment. In addition, information regarding demographics and treatment history will be collected as part of the larger study and used in this analysis.

The MDASI-BT consist of symptoms rated on an 11-point scale (0 to 10) to indicate the presence and severity of the symptom, with 0 being "not present" and 10 being "as bad as you can imagine." Each symptom is rated at its worst in the last 24 hours. Symptoms included on the instrument include those commonly associated with cancer therapies, and those associated with the underlying disease. The questionnaire also includes ratings of how much symptoms interfered with different aspects of a patient's life in the last 24 hours. These interference items include: general activity, mood, work (includes both work outside the home and housework), relations with other people, walking, and enjoyment of life. The interference items are also measured on 0 - 10 scales. The average time to complete this instrument is 5 minutes. The MDASI-BT has been translated into multiple languages, but the English language version will be used for this study[44].

3.4.2 PRO-CTCAE*:

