3.5.2 Cycle 2 Assessments

During the 2nd week of treatment, the patient will have a complete blood count (CBC) with differential and platelet count. In phase I study, if grade 3 neutropenia is identified, repeat CBC with differential every 3 days until it improves to \leq grade 2. Patient may have CBC drawn at NIH lab or outside community lab.

During the 4th week of treatment (i.e. 28-day cycle), the patient will have the following assessments:

- Physical exam with vital signs, neurological exam, neurological function score and neurological examination (including documentation of the patient's Karnofsky Performance Status), mental status score. Weight is also included.
- A Gd-DPTA enhanced MRI, with DWI, ADC, SWI, FLAIR, perfusion, dynamic contrast enhanced and dynamic susceptibility contrast sequences should be performed.
- MD Anderson Symptom Inventory-Brain Tumor Module (MDASI-BT). If the MDASI-BT is completed by the patient for Natural History study within 14 days from the MRI assessment, it can be used but only if it was administered prior to informing patient of tumor imaging results.
- Toxicity monitoring

- A complete blood count (CBC) with differential and platelet count every two weeks. In phase I study, if grade 3 neutropenia is identified, repeat CBC with differential every 3 days until it improves to \leq grade 2.
- PT, PTT, INR, total protein, albumin, calcium, phosphorus, magnesium, glucose, BUN, creatinine, sodium, potassium, total bilirubin, alkaline phosphatase, LDH, SGPT (ALT), SGOT (AST) and a pregnancy test for women of childbearing potential
- 12-lead EKG.
- Response evaluation.

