3.8 STUDY CALENDAR

Procedure	Screening/ Baseline	Cycle 1				Cycle 2				Subsequent Odd numbered cycles		Subsequent Even numbered cycles		Off- study visit ⁸
		Wk 1	Wk 2*	Wk 3	Wk 4*	Wk 1	Wk 2*	Wk 3	Wk 4*	Wk 2*	Wk 4*	Wk 2*	Wk 4*	
Informed Consent	X													
Medical History	X													
Physical Exam ¹	X				X ¹				X ¹		X ¹		X ¹	X ¹
MDASI-BT	X								X				X ⁷	
ProCTCAE***	X	X	X	X	X	X	X	X	X	X	X	X	X	
GD-DPTA MRI of brain	X								X				X ⁶	
Hematology ²	X		X		X		X		X	X	X	X	X	X
Chemistry ³	X				X				X		X		X	X
PT/PTT/INR	X				X				X		X		X	
12-lead EKG	X				X				X				X	
Pregnancy Test ⁴	X				X				X		X		X	X
Tumor Pathology	X													
Paraffin Tissue block ⁵	X													
Response evaluation									X				X	
Research samples (PK, PG, neutrophil) ^{9,10}		X ^{9,10}												

1. Physical examination includes vital signs, neurological exam, neurological function score, Karnofsky performance score, mental status score. Height and weight are also included. **Height measured only at baseline.**
2. Includes CBC with differential and platelets. In phase I study, once grade 3 neutropenia is identified, CBC with differential will be tested every 3 days until it improves to \leq grade 2.
3. Includes: Total protein, albumin, Ca, Mg, P, glucose, BUN, creatinine, Na, K, total bilirubin, alkaline phosphatase, LDH, SGPT (ALT), SGOT (AST).
4. Only for women of childbearing potential as defined in section 15.2. To be performed before each new cycle of therapy.
5. If a tissue block is unavailable, unstained slides are acceptable.
6. Brain MRI w/wo contrast needs to be done every two cycles of treatment.
7. MDASI-BT questionnaire needs to be completed at imaging cycles within +/- 1week. (prior to imaging results having been discussed with the patient). If the MDASI-BT is completed by the patient for Natural History study (CC 16C0151) within 14 days from the MRI assessment, it can be used but only if it was administered prior to informing patient of tumor imaging results.
8. If patient does not return for 30-day safety visit, patient will be taken off study for reason listed in section 3.10.3 If patient does not return, physical exam and blood work is not mandatory.

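### Section 10.2.1 accepts MDASI-BT forms on timing alone, so forms completed after the patient has heard the MRI result can enter the analysis; its ten-day tolerance also has two readings

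*Combined protocol and SAP*

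**What the plan says.** **Collection rules.**

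- Section 3.4.1 covers the trial's own forms: "every attempt should be made to administer the MDASI-BT prior to informing the patients about the results of the imaging study". This is a best effort.
- Study calendar (3.8), footnote 7, is firmer: "MDASI-BT questionnaire needs to be completed at imaging cycles within +/- 1week. (prior to imaging results having been discussed with the patient").
- Section 3.5.2 allows a substitute: "If the MDASI-BT is completed by the patient for Natural History study within 14 days from the MRI assessment, it can be used". It adds a condition, which footnote 7 repeats: "it can be used but only if it was administered prior to informing patient of tumor imaging results".

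**Analysis rules (10.2.1).**

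- Forms are "considered as valid if they fall within ten days of the scheduled assessment window".
- The stated use of this label is in the completion measure: "Compliance rates will be calculated as the number of received valid forms over the number of expected forms". Compliance is then compared between groups by Fisher's exact test at each time point.
- Patients "with at least one valid questionnaire will be included in the analyses".
- "All questionnaire data received after randomization will be used in the primary analyses".

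Section 10.2.1 compares mean severity and interference between responders and non-responders. The Statistical Analysis Plan text in section 10.2 adds a Cox model relating MDASI-BT to progression and a comparison between arms. Longitudinal MDASI-BT is a secondary objective (1.1.2.3).

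**The concern.** The collection sections treat knowledge of the scan result as something that can distort a symptom score, and they try to keep the form ahead of it. The analysis section does not carry that protection forward. A form completed a few days after the patient was told of progression is valid under 10.2.1 and is analysed. Nothing there excludes it, flags it or tests its influence.

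The planned contrasts are grouped largely by the information that was disclosed. Responder status and progression both rest mainly on the MRI. If hearing the result changes how patients rate their symptoms, part of the observed difference between these groups is a reaction to the news and not tumour-related symptom burden.

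A second problem is that the reference point of the ten days is unclear. This affects which forms count and therefore the compliance rates.

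**Working it through.** **1. The plan's own MDASI-BT figure.** Section 10.2 states 80% power with 40 patients for an effect size of 0.454 between time points, two-tailed alpha 0.05. For a paired t-test with 39 degrees of freedom and non-centrality 0.454 × √40, power is 0.7996, so the figure reproduces. It is not in dispute. It describes a within-patient change, so it is not a yardstick for a between-group bias.

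**2. Disclosure, rule by rule.**

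| Place | Forms covered | Condition on disclosure |
|---|---|---|
| 3.4.1 | Trial's own forms | Best effort to precede the result |
| 3.8, footnote 7, first sentence | Forms at imaging cycles | Must precede discussion of the result |
| 3.5.2 and footnote 7 | Borrowed Natural History forms | Usable only if before disclosure |
| 10.2.1, validity | All received forms | None |
| 10.2.1, data used | All forms after randomization | None |

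A post-disclosure form inside the tolerance passes both analysis rules. A post-disclosure form outside the tolerance fails validity but still falls under the last rule. Changing only the validity sentence would therefore not close the gap.

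Section 3.10.2 also schedules an MDASI-BT at the safety visit about 30 days after the last dose. Patients stopped for progression will normally know their result by then. Footnote 7 does not bar that form, because it does not belong to an imaging cycle, but the analysis rule does not distinguish it either.

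**3. Timing.** Count days either side of the scheduled date and treat the MRI as falling on that date. Reading A runs the ten days from the scheduled date. Reading B adds them to the ±7-day window: 7 + 10 = 17.

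| Days | Calendar (±7) | Borrowing rule (14) | 10.2.1, reading A (±10) | 10.2.1, reading B (±17) |
|---|---|---|---|---|
| 0–7 | in | in | valid | valid |
| 8–10 | out | in | valid | valid |
| 11–14 | out | in | not valid | valid |
| 15–17 | out | out | not valid | valid |

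The only clash between a form declared usable and a form declared invalid is a borrowed form at days 11–14 under reading A.

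**4. Size.** The bias in a progressor versus non-progressor contrast is (share of forms completed after disclosure) × (difference in score shift between bad and good news). The documents give neither factor, so it cannot be computed.

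Its relative size in the arm comparison can be indicated. Assume exponential PFS, with the same late share and news effect in both arms. Take a scan at 8 weeks (1.84 months), the plan's 3-month control median, and 5 months, the most favourable median in Table 15.

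- Progressed by the scan, control: 1 − 0.5^(1.84/3) = 0.346
- Progressed by the scan, combination: 1 − 0.5^(1.84/5) = 0.225
- Difference: 0.346 − 0.225 = 0.121

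The arm contrast would inherit about 12% of whatever bias the progressor contrast carries. If late completion differed by arm in this open-label comparison, that ratio would not hold.

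**The case against.** The strongest reply is that 10.2.1 checks forms against the timing schedule, that this schedule is the calendar, and that footnote 7 therefore applies without being restated. This carries some weight, since an analysis section need not repeat every collection rule. But the same sentence defines its own tolerance, which is not footnote 7's one week, so the footnote is evidently not adopted as it stands. The rule using all post-randomization forms has no such link.

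Other points stand and limit the finding:

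- **A general bar in 3.5.2.** A reader might infer one. The condition there covers only borrowed Natural History forms. The general requirement is in footnote 7, whose marker sits on the later even-numbered cycles although its wording covers imaging cycles, and 3.4.1 softens it. The protocol is itself inconsistent on whether this is a bar or a best effort.
- **Three contradictory windows.** A reader might infer this from 7, 10 and 14 days. They serve different purposes: completing a form, checking it for analysis, and borrowing one. An analysis tolerance wider than a visit window is not an error.
- **Legitimate forms discarded.** This holds only under reading A, and only for validity and compliance. The rule using all forms would still admit them.
- **Removing late forms.** If forms tend to be late when a scan shows progression, excluding them selectively removes progressors' data. Exclusion as the only main approach is therefore debatable.

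**Conclusion.** The concern holds in limited form. As written, 10.2.1 admits MDASI-BT forms that footnote 7 and the borrowing condition disallow, and it does not say how they are handled. This may bias the responder versus non-responder comparison.

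For the Cox model the effect depends on a choice that the plan leaves open. With baseline scores, post-result forms play no part. With properly built time-dependent scores and progression dated to the scan, a form completed after hearing of that progression falls after the event. A reader might infer that late forms create an association with progression by construction; the documents do not support that, because the model is not specified.

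Nor do they support a figure for the bias in SD units, since any late share or news effect would be pure assumption. The between-arm effect is probably small, given similar late completion in the two arms. Primary PFS, dose selection and the stopping rules do not use MDASI-BT. The ambiguity between ±10 and ±17 days is real, and its clear consequence is limited to borrowed forms at days 11–14.

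**What to change.** In 10.2.1:

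- Add completion before disclosure of that visit's imaging result to the definition of a valid on-study form.
- State one tolerance and its reference date, consistent with footnote 7 and with the 14-day borrowing rule.
- Say whether the analyses use valid forms or all forms after randomization, and use the same set throughout.
- Report the MDASI-BT analyses with and without post-disclosure forms.
- In the Cox model, use only scores completed before the patient was told the result of the scan that dates progression. Section 3.10.1 allows progression to be dated back to an earlier MRI, so the rule should refer to that scan.

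Elsewhere, align 3.4.1 with footnote 7. Add a yes/no field to the form for whether the result had already been given, including on the off-study form. The field should be in place before phase II forms are collected, because disclosure status is hard to reconstruct later.

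The cost is wording, one extra field and one sensitivity analysis. The analysis that excludes post-disclosure forms may lose progressors' forms selectively, which is why both versions should be reported.

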- 2.1.1.11 Patients must have recovered from the toxic effects of prior therapy to < grade 2 toxicity per CTC version 4 (except deep vein thrombosis)
- 2.1.1.12 At the time of registration, subject must be removed from prior therapy as follows:
- ≥ 28 days from any investigational agent,
 - ≥ 4 weeks (28 days) from prior cytotoxic therapy,
 - ≥ 2 weeks (14 days) from vincristine,
 - ≥ 6 weeks (42 days) from nitrosoureas,
 - ≥ 3 weeks (21 days) from procarbazine administration,
 - ≥ 1 week (7 days) for non-cytotoxic agents, e.g., interferon, tamoxifen, thalidomide, cis-retinoic acid, etc. (radiosensitizer does not count).
- 2.1.1.13 Patients having undergone recent resection of recurrent or progressive tumor will be eligible given all of the following conditions apply:
- A. At least 2 weeks (14 days) have elapsed from the date of surgery and the patients have recovered from the effects of surgery.
- B. Evaluable or measurable disease following resection of recurrent malignant glioma is not mandated for eligibility into the study.
- C. To best assess the extent of residual disease post-operatively, an MRI should be done no later than 96 hours in the immediate post-operative period or at least within 4 weeks post-operatively, within 14 days prior to registration. If the 96-hour scan is more than 14 days before registration, the scan needs to be repeated. The patient must have been on a stable steroid dose for at least 5 days prior to the baseline MRI. Steroids may be initiated as clinically indicated once baseline imaging has been completed with a goal of titrating steroids as soon as clinically warranted.
- 2.1.1.14 Patients must have received prior radiation therapy and must have an interval of greater than or equal to 12 weeks (84 days) from the completion of radiation therapy to study entry except if there is unequivocal evidence for tumor recurrence (such as histological confirmation or advanced imaging data such as PET scan) in which case the principal investigator's discretion may determine appropriate timepoint at which study therapy may begin.

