6.3.2 Definitions

Evaluable for maximum tolerated dose: All subjects enrolled in the Phase I dose escalation cohorts from the time of their first treatment with Zotiraciclib (TG02) +TMZ to the end of cycle 1. Patients who develop a DLT during cycle 1 and thus do not complete treatment for the cycle should be considered evaluable for MTD.

Evaluable for toxicity: All eligible patients who complete at least one cycle of protocol therapy or who have a DLT after the protocol therapy is started are evaluable for toxicity from the time of their first treatment.

*If the patients miss doses of Zotiraciclib (TG02) or TMZ in the first cycle of treatment due to reasons that are unrelated to toxicity, it will be the PI's decision about whether they are evaluable for toxicity in the dose finding stage.

Evaluable for objective response: Only those patients who have measurable disease present at baseline, have received at least one cycle of therapy at MTD and have had their disease re-evaluated will be considered evaluable for response. These patients will have their response classified according to the definitions stated below. (Note: Patients who exhibit objective disease progression prior to the end of cycle 1 will also be considered evaluable.)

Phase I patients removed from study treatment within 28 days for reasons other than toxicity may be replaced.

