6.3.3 Disease Parameters

Measurable Disease: Bi-dimensionally measurable lesions with clearly defined margins by GD-DPTA enhanced MRI scan.

Evaluable Disease: Uni-dimensionally measurable lesions, masses with margins not clearly defined. Patients with only this kind of imaging will not be allowed to enter this study unless they have recently undergone surgery and have histologically proven recurrent disease.

Non-Evaluable Disease: Not Applicable for response evaluation.

Objective-Status, To Be Recorded at Each Evaluation: If there are too many measurable lesions to measure at each evaluation, choose the largest two to be followed before a patient is entered on study. The remaining lesions will be considered evaluable for the purpose of objective status determination. Unless progression is observed, objective status can only be determined when ALL measurable and evaluable sites and lesions are assessed.

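### The responder versus non-responder MDASI-BT comparison is set in a population that the response definition does not cover, and it can favour responders even if response has no effect on symptoms

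*Combined protocol and SAP*

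**What the plan says.** - **Comparison.** Section 10.2.1 (Patient Reported Outcomes) estimates differences in mean symptom severity and mean interference "between responders and non-responders will be estimated in the intent to treat population". It does not define a responder. For this contrast it gives no landmark, time-dependent status, baseline covariate or test.
- **Data used.** The same section states "All questionnaire data received after randomization will be used in the primary analyses", and that all patients "with at least one valid questionnaire will be included in the analyses". The second rule already departs from a strict intention-to-treat set.
- **Who can be classified.** Section 6.3.2 limits response to "Only those patients who have measurable disease present at baseline, have received at least one cycle of therapy at MTD" and a disease re-evaluation.
- **Who can enrol.** Section 2.1.1 (item 2.1.1.13) says "Evaluable or measurable disease following resection of recurrent malignant glioma is not mandated for eligibility into the study". Section 6.3.3 says of evaluable-only disease: "Patients with only this kind of imaging will not be allowed to enter this study unless they have recently undergone surgery". Sections 2.3.1 and 10.2 stratify randomization by measurable disease, so patients without it are expected.
- **Timing.** Section 3.5.2 puts the first on-treatment MRI, the first response evaluation and the "MD Anderson Symptom Inventory-Brain Tumor Module (MDASI-BT)" together in week 4 of cycle 2. Section 6.3.5 repeats response evaluation every 2 months.
- **Response definition.** Section 6.3.4 requires stable or improved clinical status for both complete and partial response, sustained for at least 4 weeks.
- **Threshold.** Section 10.2.1 sets 2 points as the minimum meaningful change.

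**The concern.** There are two problems.

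1. **Population.** A two-way split of all randomized patients needs a response status for everyone, but section 6.3.2 supplies one only for a subset. The analysis cannot be run without a decision that the plan does not record, and that decision moves the estimate.
2. **Grouping.** To be a responder a patient must reach the week 8 scan without progression and be clinically stable or better. Patients who progress earlier fall on the other side, and the form from their progression visit counts there. If symptoms track prognosis or worsen at progression, a gap appears with no effect of response.

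Symptom burden is a secondary objective (section 1.1.2.3), and section 1.2.8 presents such instruments as a further sign of benefit. A better score in responders could therefore be taken as relief produced by tumour response, when part or all of it separates early progressors from the rest.

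**Working it through.** **1. The plan's own MDASI-BT figure.** Section 10.2 gives 80% power for n = 40, effect size 0.454, two-sided alpha 0.05. A paired t-test (noncentral t) gives 0.7996, so it reproduces. It concerns change between time points. No figure is given for responders versus non-responders.

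**2. Early progressors.** Input: control median PFS of 3 months (section 10.2). With exponential PFS, P(progressed by month 2) = 1 − 2^(−2/3) = 0.370. Medians of 2 and 5 months give 0.50 and 0.24. The phase I interim PFS4 values in section 10.1 (38% and 25%) imply, under the same assumption, 1 − √0.38 = 0.38 and 1 − √0.25 = 0.50.

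**3. Spurious difference when response has no effect.** Simulation, 1,500 runs per setting. From the documents: 80 patients, median PFS 3 months, scan and form every 2 months. Assumed: last form at the first scan after progression; response possible only if progression-free at month 2; latent response propensity 30% (20% in the no-link row); between-patient SD 1.5 and within-patient SD 1.0. Prognosis strength r is the correlation of a common factor with symptoms and with response propensity, and its log hazard per SD for progression. Entries are responders minus non-responders in points; negative means fewer symptoms in responders. All patients are measurable here.

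| Setting | As planned | Month-2 landmark, unadjusted |
|---|---|---|
| No link | 0.01 | 0.02 |
| Rise at progression 0.5 | −0.15 | 0.02 |
| Rise 1 | −0.33 | −0.01 |
| Rise 2 | −0.59 | 0.01 |
| r = 0.3 | −0.28 | −0.23 |
| r = 0.5 | −0.70 | −0.57 |
| r = 0.7 | −1.28 | −1.05 |
| r = 0.3, rise 1 | −0.60 | −0.26 |
| r = 0.5, rise 1 | −1.06 | −0.65 |

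In the last two rows a nominal 5% t-test, had one been planned, would reject 21% and 59% of the time. With shared prognosis alone the gap is already there at baseline (−0.27, −0.70, −1.26 for r = 0.3, 0.5, 0.7). That is why a landmark alone does not remove it and the baseline score is needed.

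**4. Patients without measurable disease counted as non-responders** (r = 0.3, rise 1; share and symptom shift assumed):
- 20%, same symptoms: −0.58
- 20%, 1 point lower: −0.31
- 40%, 1 point lower: −0.08
- 40%, 2 points lower: +0.36

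**5. Effect of the fix.** A separate null simulation with its own assumed inputs (20% without measurable disease, median PFS 3 months) gives a spurious advantage of 0 to 1.3 points as planned, 0 to 0.55 with a landmark alone, and 0 to 0.25 with a baseline-adjusted landmark. The last figure is not a ceiling. With the SDs in step 3 a single baseline form has reliability 1.5²/(1.5² + 1.0²) = 0.69, so adjustment at r = 0.7 would leave roughly 1.05 × 0.31 = 0.33.

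**6. Patients left.** 80 × 0.80 measurable × 0.63 progression-free = 40. At an assumed 20% response that is 8 responders; the simulation in step 5 gave 9 to 11. With 8 against 32, the 95% half-width is about 1.96 × √(1/8 + 1/32) = 0.77 SD.

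**The case against.** The best defence is that section 10.2.1 never says patients are grouped by whether they ever respond. Forms are completed at imaging visits, and section 6.3.6 records a response from the scan that shows it, so status and form could be paired visit by visit with no later information. Section 6.3.6 also has an unknown category, so non-evaluable patients might be left unclassified. The contrast is called an estimate, carries no test and drives no decision. Describing symptoms by tumour status may properly include progressors.

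Much of this stands, and it rules out three stronger readings:
- **That responders will necessarily look better.** The documents quantify no link between symptoms and prognosis or progression, and without one the bias is zero.
- **That the plan counts patients who cannot respond as non-responders.** This is the natural reading of a two-way split, but it is not written. Those patients are mainly recently resected. If they have fewer symptoms, including them works against the first bias.
- **That the trial's symptom conclusions are compromised.** Section 10.2 compares MDASI-BT by randomized arm separately.

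The defence does not remove the point. Visit-by-visit pairing is not specified, and it would still set forms taken at progression against those of responders. Leaving non-evaluable patients unclassified contradicts the stated population. A link is also plausible on the plan's own terms: clinical status is part of the response definition, clinical decline is a progression criterion (Appendix 15.5), and section 10.2 plans a Cox model relating MDASI-BT to progression.

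**Conclusion.** The point holds in conditional form. The stated population conflicts with section 6.3.2, and the comparison as described can show better symptoms in responders even if response does nothing. The bias is zero with no link, 0.15 points at the weakest link tried, and roughly 0.3 to 1.3 points under the other assumed links. All of these are below the 2-point threshold. Counting patients without measurable disease as non-responders could shrink or reverse it.

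The 37% rests on the plan's 3-month median and exponential PFS. The symptom SDs, response propensity, share without measurable disease and strength of the links are assumptions, not figures from the documents. This is an untested secondary estimate, and neither the primary PFS analysis nor the by-arm MDASI-BT comparison depends on it.

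**What to change.** For this comparison only, in section 10.2.1:

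1. Replace the intention-to-treat population with the response-evaluable population of section 6.3.2, and define responder. Section 6.3.2 refers to therapy at the MTD, so word the definition to fit the control arm too.
2. Classify response at the week 8 scan among patients progression-free at that scan, or use response status as a time-dependent covariate so that later responders are kept.
3. Compare only subsequent severity and interference scores, with the baseline score as covariate.
4. Label the result descriptive, not a symptom benefit of response.

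Keep the by-arm MDASI-BT comparison in all randomized patients.

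**Cost.** This is SAP wording and uses data already collected. About 40 patients and roughly 8 to 11 responders remain on the assumed inputs, so the interval will be wide. A fixed week 8 landmark counts delayed responders as non-responders, and section 3.10.1 reports delayed imaging responses; the time-dependent version avoids this. Some bias, up to about 0.25 points in simulation and more if the link to prognosis is very strong, can remain after baseline adjustment.
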